### 9.7.2. Disease Progression

A subject will have met the criteria for disease progression when one or more of the following events have occurred:

- Death from respiratory failure, or
- Absolute decrease of  $\geq 10\%$  from baseline in percent predicted FVC at two consecutive evaluations at a minimum of 4 weeks between evaluations, or
- Decrease from baseline of  $\geq 50$  meters in 6MWT distance (in the absence of a readily explainable cause, such as injury or trauma), or
- Unexplained worsening hypoxemia (an absolute decrease from baseline of 4% or more in SpO2).

Subjects who experience an absolute decrease of  $\geq 10\%$  from baseline in percent predicted FVC at two consecutive evaluations at a minimum of 4 weeks between evaluations must be discontinued from the study IP and enter the Post-treatment Observational Follow-up (see Section 11.1). Example: a subject whose FVC decreases from 50% predicted at Visit 2 to 40% predicted at Visits 4 and 5 must be discontinued from the study. Whether to discontinue a subject from study treatment who experiences: 1) a decrease from baseline of  $\geq 50$  meters in 6MWT distance (in the absence of a readily explainable cause, such as injury or trauma), or 2) a new or worsening hypoxemia (an absolute decrease from baseline of 4% or more in SpO2), is at the Investigator's discretion.

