**Table 1: Study Objectives (Continued)**

**Table 1: Study Objectives (Continued)**

**Table 2: Idiopathic Pulmonary Fibrosis Study Endpoints**

Endpoint	Name	Description	Timeframe
Primary	Forced vital capacity (FVC)	Percentage point difference in % predicted FVC	Baseline to Week 24
Secondary	FVC	Absolute change and rate of decline in FVC (expressed in mL)	Baseline through Week 24
Secondary	6-minute Walk Test (6MWT) with Borg Scale	Change in the distance walked during the 6MWT as measured in meters (m) Change in dyspnea rating on Borg Scale	Baseline to Week 24; Baseline to Week 52; Baseline to Week 76; Baseline to Week 104; Week 24 to Week 52; Week 24 to Week 104
Secondary	Disease progression	Disease progression is defined as one or more of the following: 
 
• Death from respiratory failure, or
 
• Absolute decrease of <math>\geq 10\%</math> from baseline in % predicted FVC at two consecutive evaluations at a minimum of 4 weeks between evaluations, or
 
• Decrease from baseline of <math>\geq 50</math> meters in 6MWT distance (in the absence of a readily explainable cause, such as injury or trauma), or
 
• Unexplained worsening hypoxemia (an absolute decrease from baseline of 4% or more in arterial oxygen saturation by pulse oximetry [SpO2]).
 
	Baseline through Week 24
Secondary	Quality of life	Change from Baseline in total score and domains on the Saint George's Respiratory Questionnaire (SGRQ)	Baseline through Week 24
		Change from Baseline in the University of California San Diego Shortness of Breath Questionnaire (UCSD- SOBQ)	Baseline through Week 24

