### 5. TABLE OF EVENTS

**Table 5: Table of Events**

	Screening Phase	24-Week Double-Blind Placebo-Controlled Treatment Phase			80-Week Active Treatment Extension Phase				Early Termination Visit	Post-Treatment Observational Follow-up
Visit(s) k	1 Screening	2 Baseline a	3	4-9 Every 4 Weeks	10E	11E-17E Every 4 Weeks	18E-25E Every 6 Weeks	26E End of Treatment		27E
Week(s)	-8 to -1	0	1 ± 3 days	4, 8, 12, 16, 20, 24 ± 3 days	25 ± 3 days	28, 32, 36, 40, 44, 48, 52 ± 3 days	58, 64, 70, 76, 82, 88, 94, 100 ± 3 days	104 ± 3 days		108 4-weeks post-treatment ± 3 days
Main Informed Consent	X	-	-	-	-	-	-	-	-	-
Inclusion/Exclusion Criteria	X	X	-	-	-	-	-	-	-	-
Demographics	X	-	-	-	-	-	-	-	-	-
Complete Medical History	X	-	-	-	-	-	-	-	-	-
Prior IPF Disease History	X	-	-	-	-	-	-	-	-	-
Prior IPF Therapies	X	-	-	-	-	-	-	-	-	-

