**Table 5: Table of Events (Continued)**

	Screening Phase	24-Week Double-Blind Placebo-Controlled Treatment Phase			80-Week Active Treatment Extension Phase				Early Termination Visit	Post-Treatment Observational Follow-up
	1 Screening	2 Baseline a	3	4-9 Every 4 Weeks	10E	11E-17E Every 4 Weeks	18E-25E Every 6 Weeks	26E End of Treatment		
Week(s)	-8 to -1	0	1 ± 3 days	4, 8, 12, 16, 20, 24 ± 3 days	25 ± 3 days	28, 32, 36, 40, 44, 48, 52 ± 3 days	58, 64, 70, 76, 82, 88, 94, 100 ± 3 days	104 ± 3 days		108 4-weeks post-treatment ± 3 days
Spirometry g	X	X	X	X	X	X	X	X	X	X
SpO 2 g	X	X	X	X	X	X	X	X	X	X
UCSD-SOBQ	-	X	-	Weeks 12, 24						
D L CO g	X	X	-	Week 24	-	Week 52	-	X	X	X
6MWT with Borg Scale	X	X	-	Week 24	-	Week 52	Week 76	X	X	X
Assessment for New or Worsening Shortness of Breath	X	X	X	X	X	X	X	X	X	X

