g Spirometry, DLCO, and pulse oximetry will be assessed as part of the safety assessments for those subjects who discontinue for progressive disease during the 24-Week Double-blind Placebo-controlled and 80-Week Active Treatment Extension Phases.

- i Blinded IP will be packaged in 32 tablet-count, 16-day blister cards (16-day card includes IP for two additional days in the event the subject is unable to return for their scheduled visit).
  - On Visits 2 and 3, one blister card will be dispensed to the subject. Remaining IP from the blister card issued on Visit 2 will be reissued to the subject along with a new card on Visit 3. The subject should be instructed to finish the remaining IP in the blister card issued at Visit 2 before starting the new blister card issued at Visit 3.
  - On Visits 4 to 8, two blister cards will be dispensed to the subject per visit.
  - On Visits 9 and 10E, one blister card will be dispensed to the subject. Remaining IP from the blister card issued on Visit 9 will be reissued to the subject along with a new card on Visit 10E. The subject should be instructed to finish the remaining IP in the blister card issued at Visit 9 before starting the new blister card issued at Visit 10E.
  - On Visits 11E to 16E, two blister cards will be dispensed to the subject per visit.
  - On Visit 17E to 24E, three blister cards will be dispensed to the subject per visit.
  - On Visit 25E, two blister cards will be dispensed to the subject per visit.
- j Final dose of IP administered at the investigative site.
- k For all subsequent visits, an administrative window of  $\pm 3$  days is permitted. Scheduling of Visits 3 to 9 is based on Visit 2 (randomization date) and scheduling of Visits 10E to 26E is based on Visit 9 (re-randomization date). The Post-treatment Observational Follow-up Visit is scheduled 28 days (4 weeks) after the date of the last dose of IP  $\pm 3$  days.
- l If a subject has adequate documentation of successful treatment for either latent or active TB, the QuantiFERON-TB Gold test is not needed. Instead, a chest radiograph, obtained within the 12 weeks prior to Screening or during Screening, without changes suggestive of active TB infection as determined by a qualified radiologist, will be sufficient to permit further participation in the study for these subjects. Documentation of adequate treatment for TB must be obtained prior to randomization.

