## 6.2. Treatment Phase

The subject will begin treatment upon confirmation of eligibility at the Baseline (Visit 2). For all subsequent visits, an administrative window of  $\pm 3$  days is permitted. Scheduling of Visits 3 to 9 is based on Visit 2 (randomization date) and scheduling of Visits 10E to 26E is based on Visit 9 (re-randomization date).

The following evaluations will be performed at the frequency specified in the Table of Events, [Table 5](#) and in the order described below. The evaluations should be performed prior to dosing on the visit day, unless otherwise specified.

- Adverse event evaluation
- Concomitant medications reviewed with the subject
- Concomitant procedures reviewed with the subject
- Patient-reported outcome questionnaires will be completed as described in [Section 6.7](#)
- Assessment for new or worsening shortness of breath

As part of the routine assessments during the study visit, subjects will be assessed for new or worsening of shortness of breath (SOB). The Investigator should use his/her clinical judgement to decide how to further assess and treat such subjects.

Subjects who experience and receive adequate treatment for SOB with permitted drugs (see [Section 8.1.2](#)) but demonstrate further clinical decline and/or decrease of  $\geq 10\%$  from baseline in % predicted FVC at two consecutive evaluations at a minimum of 4 weeks between evaluations should discontinue IP and enter the 4-week Post-treatment Observational Follow-up Phase (Table of Events, [Table 5](#)). Whether to discontinue a subject from study treatment who experiences unexplained worsening in hypoxemia (an absolute decrease from baseline of 4% or more in SpO2) will be left up to the Investigator's discretion. Treatment of subjects during the Post-treatment Observational Follow-up Phase is at the discretion of the Investigator.

All relevant clinical data (summary on clinical course, signs and symptoms; laboratory, lung function and imaging results; and treatment provided) relating to new or worsening shortness of breath must be collected by the Investigator. Changes in respiratory status that are considered by the Investigator as possibly or likely due to [REDACTED] disease progression will be reviewed further by the independent Adjudication Committee. Details regarding the adjudication process will be described in a separate charter.

- Efficacy assessments as described in [Section 6.4](#)

- 

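### Do the ±3-day visit windows undermine the 4-week confirmation rule for the FVC fall in the disease progression endpoint?

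*Combined protocol and SAP*

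**What the plan says.** Disease progression is a secondary endpoint with four alternative components: death from respiratory failure, a confirmed FVC fall, a 6-minute walk fall of 50 metres or more, and an SpO2 fall of 4% or more. Only the FVC component needs a second reading. Table 2 asks for the fall "in % predicted FVC at two consecutive evaluations at a minimum of 4 weeks between evaluations", Section 9.7.2 repeats the condition ("in percent predicted FVC at two consecutive evaluations at a minimum of 4 weeks between evaluations"), and Section 6.2 uses it again in its text on stopping investigational product (IP). None of the three gives a tolerance in days.

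Section 9.7.2 adds an example: a subject who falls from 50% predicted at Visit 2 to "40% predicted at Visits 4 and 5 must be discontinued from the study". It puts no condition on the dates of those two visits.

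Table 5 presents Visits 4 to 9 as a four-weekly block, at weeks "4, 8, 12, 16, 20, 24 ± 3 days". Section 6.2 introduces the tolerance with the words "For all subsequent visits, an administrative window of" ±3 days and counts Visits 3 to 9 from Visit 2, not from the preceding visit. Spirometry is done at every visit, including the one headed "Early Termination Visit". Section 9.6.2.1 compares the proportion progressing at Week 24 with a CMH test. Section 9.1 leaves analysis details to a separate SAP, to be written before unblinding. That SAP was not in the material examined.

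**The concern.** The confirmation interval equals the nominal visit spacing, which leaves no slack. Because each visit is timed from Visit 2, the gap between two compliant visits shortens whenever the later one falls earlier in its window than its predecessor did. Read as at least 28 days, the rule would then reject a pair that is fully on schedule. Whether a repeated 10-point fall counts as an event could depend on the day the subject attended.

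The exposed case is a fall first seen at Week 20 and repeated at Week 24. The endpoint window closes there, so no later pair can rescue it. If many events were lost this way, or more in one arm than another, the Week 24 comparison would suffer. That comparison also matters for dose selection, since Section 9.9.3 says secondary endpoints will help inform it.

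**Working it through.** **The plan's own figure.** The plan gives no progression rate and no power for this endpoint. Its one design figure is the 75% power for the primary endpoint in Section 9.3 (55 per arm, difference 2.2, SD 5, two-sided alpha 0.1). It reproduces: 2.2 / (5 × √(2/55)) = 2.2 / 0.953 = 2.307; 2.307 − 1.645 = 0.662; power = Φ(0.662) = 74.6% (74.2% with the noncentral t). The confirmation rule does not enter it.

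**Gap between adjacent visits.** Let the earlier visit be *a* days and the later *b* days off schedule, each from −3 to +3. The gap is 28 + *b* − *a*, so it runs from 28 − 6 = 22 to 28 + 6 = 34 days. Of the 7 × 7 = 49 combinations, 7 give exactly 28 days, 21 give more and 21 give fewer. A strict 28-day count rejects 21/49 = 42.9% if all offsets are equally likely. A scheduled-visit reading rejects 0 of 49.

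**Chance that every pair fails in a sustained fall** (independent uniform offsets; the offsets must strictly decrease from visit to visit):
- one pair: 21/49 = 42.9%
- two pairs: 35/343 = 10.2%
- three pairs: 35/2401 = 1.5%

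Only late falls are materially exposed.

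**Effect on the FVC component.** The documents supply the SD of 5 and the 55 per arm. The rest is assumed: mean Week 24 changes of −1.5, −3 and −5; FVC following either a random walk or a random slope with reading error of SD 2; and several patterns of attendance. Under these, 1.7% to 9.2% of subjects (0.9 to 5.1 per arm) have a 10-point fall at two consecutive visits between Weeks 4 and 24. For 51% to 62% of them, Weeks 20 and 24 are the only pair.

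| Assumed attendance | Chance a pair is under 28 days | Share of FVC events missed | Subjects per arm of 55 |
|---|---|---|---|
| Same offset at every visit | 0 | 0% | 0 |
| 90% on the subject's usual offset | (1 − 0.9²) × 21/49 = 0.081 | 4.6–5.6% | 0.05–0.2 |
| 80% on the exact day | 0.177 | 10.3–12.5% | 0.1–0.5 |
| 70% on the usual offset | (1 − 0.7²) × 21/49 = 0.219 | 12.8–15.4% | 0.1–0.6 |
| 50% on the exact day | 0.354 | 21.7–25.8% | 0.2–1.1 |
| Independent uniform | 0.429 | 27.1–31.9% | 0.3–1.4 |

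The largest loss is 55 × 9.21% × 27.1% = 1.4 subjects. A second simulation, with linear decline of 2 to 5 points and reading error of SD 1.5 to 3.3, lost 11% to 34% of FVC events, or 0.1 to 1.3 subjects per arm.

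**Effect on the comparison.** The risk ratio is multiplied by the ratio of the shares retained. With uniform timing:
- −1.5 versus −5: (1 − 0.293)/(1 − 0.271) = 0.97 (walk) and (1 − 0.319)/(1 − 0.298) = 0.97 (slope)
- −3 versus −5, a 2-point difference close to the 2.2 assumed in Section 9.3: 0.716/0.729 = 0.98 and 0.691/0.702 = 0.98

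**Which reading the text supports.** The schedule itself calls these visits four-weekly and treats the ±3 days as administrative. The example accepts Visits 4 and 5 outright. On that reading the word minimum still does work. It excludes Week 1 with Week 4 (25 − 10 = 15 to 31 − 4 = 27 days), and it can exclude an early repeat or an early-termination reading taken soon after a visit.

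**The case for a change.** The best argument for a change is that the text supports two readings and a programmer has to choose. The rule states a minimum interval; the example ignores dates, and it illustrates stopping IP rather than the endpoint. Under a strict count with scattered attendance, up to about a third of FVC-component events could go uncounted. One sentence would settle it: accept adjacent in-window four-weekly visits, or any consecutive evaluations at least 28 days apart. It would need no new data and would lose no pair that qualifies now.

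Part of this stands. The wording is undefined, and a third of one component is not trivial in relative terms. The rest is weaker. The example appears in the same section and illustrates the same phrase, so it is fair evidence of what the phrase means. The large losses need both the unstated strict reading and widely scattered attendance. Visits are scheduled under blinding, so there is no evident reason for timing to differ by arm. Section 9.1 requires the details to be fixed before unblinding, so the choice need not be made with results in view. Changing the endpoint wording alone would also give one phrase two meanings, because the same words govern stopping IP.

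On stopping IP, the passages do differ. Section 6.2 says such subjects should discontinue IP. Section 9.7.2 says they must, and its example speaks of leaving the study. Section 11.1, which Section 9.7.2 cites, lists disease progression as a sufficient reason and leaves the decision to the treating physician. The sponsor must reconcile these passages. That does not depend on the day count, and no clinical rule is proposed here.

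**Conclusion.** No change to the plan follows. The arithmetic behind the concern is right, but it bites only if 4 weeks is read as a strict 28-day count, which no passage states and which the visit schedule and the worked example speak against. On the scheduled-visit reading nothing is lost. What remains is a missing derivation detail of the kind routinely settled in a SAP, and the separate SAP may already settle it.

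On the strict reading the cost is 0 to 1.4 subjects per arm in the FVC component, with a risk-ratio multiplier of 0.97 to 1.00. These ranges depend on assumed decline, reading error and attendance, none of which the documents give. The effect on the composite was not estimated. It cannot exceed the component's loss, because some missed subjects would still count through the walk-distance or SpO2 criteria. The primary endpoint and its power are untouched.

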### 9.8. Interim Analysis

An initial interim analysis will be conducted after approximately 50 non-SOC subjects with IPF have completed 24 weeks of treatment. The purpose of this interim analysis is to

determine whether to terminate the study based on futility criteria and if futility criteria are not met, whether to discontinue any treatment group. Sample size re-estimation may be performed based on observed standard deviation and effect size.

If the safety and efficacy of CC-90001 from these initial IPF subjects are favorable, the study will continue as planned and enrollment into the PPF substudy will be initiated. Subjects enrolled into the PPF substudy will be randomized to CC-90001 400 mg PO QD, unless review of benefit-risk favors 200 mg PO QD, or placebo.

An additional unblinded interim analysis is planned after approximately 40 SOC IPF subjects have completed 24 weeks of treatment. The purpose of the additional interim analysis is to evaluate safety, tolerability and efficacy of CC-90001 in SOC IPF subjects, along with all study subjects enrolled into the study, and to determine if any treatment group should be discontinued. Sample size re-estimation may also be considered for the non-SOC group, the SOC group or subjects in the PPF sub-study.

If a decision at an interim analysis is made to discontinue a treatment group, that decision may be made separately for IPF subjects not receiving concurrent SOC and for IPF subjects receiving concurrent SOC. A decision to discontinue a treatment group will be based on lack of efficacy (ie, futility) and/or lack of acceptable safety and tolerability. If a treatment group is discontinued, subjects may receive a different CC-90001 dose regimen during the 80-week Active Treatment Extension Phase than during the 24-week Double-blind Placebo-controlled Phase.

Additional interim analyses may be conducted.

The DMC will be responsible for review of the interim analyses data and will make recommendations to a Celgene internal review committee, who will be responsible for final decision-making. The Celgene internal review committee members will not play a role in the study conduct and the blind will be maintained for persons responsible for the ongoing conduct and management of the study.

The details of these analyses, similar to analyses described in Sections 9.6.1 and 9.6.2, will be documented in a separate charter/analysis plan.

## 9.9. Other Topics

### **9.9.3. Analysis of Dose-Response**

The primary method of analysis of dose-response for efficacy will be based on the MMRM model of the primary endpoint as described in Section 9.6.1. Supportive analyses, including sensitivity analyses and analyses of secondary endpoints, as described in Section 9.6.2, will also help inform optimal dose selection. The overall benefit-risk profile for each dose will be used to determine the dose(s) selected for further clinical development.

### **9.9.4. External Data Monitoring Committee**

Although the Celgene study staff will monitor safety on an ongoing basis throughout the study, formal unblinded safety and efficacy assessments of the study data will be performed by an independent external DMC. The DMC is comprised of independent physician experts and a statistician who are not affiliated with the Sponsor and for whom there is no identified conflict of interest. The scope, conduct, membership, processes, and accountabilities of the DMC are specified in the DMC charter.

The DMC will be also responsible for review of the interim analyses data and will make recommendations to a Celgene internal review committee (IRC), who will be responsible for final decision-making. The Celgene IRC members will not play a role in the study conduct and the blind will be maintained for persons responsible for the ongoing conduct and management of the study. The details of this analysis including the scope of distribution will be documented in a separate charter/analysis plan.

### **9.9.5. Celgene Safety Management Team**

In addition to safety monitoring conducted by Investigators, site study personnel, and by the Celgene study team, blinded study safety data will be reviewed by the Celgene SMT. The SMT is comprised of lead representatives from multiple Celgene functions engaged in the CC-90001 development program.

## **10. ADVERSE EVENTS**

### **10.1. Monitoring, Recording and Reporting of Adverse Events**

An AE is any noxious, unintended, or untoward medical occurrence that may appear or worsen in a subject during the course of a study. It may be a new intercurrent illness, a worsening concomitant illness, an injury, or any concomitant impairment of the subject's health, including laboratory test values (as specified by the criteria in Section 10.3), regardless of etiology. Any worsening (ie, any clinically significant adverse change in the frequency or intensity of a pre-existing condition) should be considered an AE. A diagnosis or syndrome should be recorded on the AE page of the CRF rather than the individual signs or symptoms of the diagnosis or syndrome.

Abuse, withdrawal, sensitivity or toxicity to an investigational product should be reported as an AE. Overdose, accidental or intentional, whether or not it is associated with an AE should be reported on the overdose CRF. (See Section 7.2 for the definition of overdose.) Any sequela of an accidental or intentional overdose of an investigational product should be reported as an AE on the AE CRF. If the sequela of an overdose is an SAE, then the sequela must be reported on an SAE report form and on the AE CRF. The overdose resulting in the SAE should be identified as the cause of the event on the SAE report form and CRF but should not be reported as an SAE itself.

In the event of overdose, the subject should be monitored as appropriate and should receive supportive measures as necessary. There is no known specific antidote for CC-90001 overdose. Actual treatment should depend on the severity of the clinical situation and the judgment and experience of the treating physician.

All subjects will be monitored for AEs during the study. Assessments may include monitoring of any or all of the following parameters: the subject's clinical symptoms, laboratory, pathological, radiological or surgical findings, physical examination findings, or findings from other tests and/or procedures.

All AEs will be recorded by the Investigator from the time the subject signs informed consent until 28 days after the last dose of IP as well as those SAEs made known to the Investigator at any time thereafter that are suspected of being related to IP. AEs and SAEs will be recorded on the AE page of the CRF and in the subject's source documents. All SAEs must be reported to Celgene Drug Safety within 24 hours of the Investigator's knowledge of the event by facsimile, or other appropriate method, using the SAE Report Form, or approved equivalent form.

